### ***8.3. Method of Assigning Subjects to Treatment Arms***

Subjects will be assigned to the Clareon monofocal or the LAL treatment groups in a 1:1 ratio using the method of randomly permuted blocks.

## **9. STUDY PROCEDURE**

### ***9.1. Informed Consent / Subject enrollment***

No subject will be enrolled into the study who does not meet the inclusion/exclusion criteria and does not sign the current approved informed consent document. Informed consent will be obtained prior to collecting any data for the study. The original signed documents will be maintained by the investigator as a permanent part of the subject's medical records. A signed copy will be provided to the subject.

### ***9.2. Visits and Examinations***

Subjects will participate in eight study visits, one eye per visit for bilateral surgery. Visits will include an uptake visit, two operative visits, and up to 6 total postoperative visits (Visit numbers 1-8 below). The visit schedule, complete with window and associated CRF forms, are displayed in Table 9.2-1. Details of each study visit, including testing to be conducted, are provided below.

**Table 9.2-1. Visit Schedule**

Visit Number	Visit Name	Visit Window	Group	CRF Number
1	Preoperative	-90 to 0 days from surgery	L,C	1
2,2a	Operative	0 from surgery	L,C	2,2a
3	Follow Up Visit and LAL with UV treatment #1	POD 17-28	L,C	3
4	LAL with UV treatment #2 or lock-in #1	POD 24-42	L	4
5	LAL with UV treatment #3 or lock-in #1 or lock-in #2	POD 31-56	L	5
6	LAL with lock-in #1 or LAL lock-in #2 (if needed)*	POD 38-63	L	6
7	LAL with lock-in #2 (if needed)*	POD 45-70	L	7
8	Final Visit	POD 90 ± 14 days	L,C	8

C = Clareon Group; L = LAL Group; POD = postoperative day

\*Note that visits 6 and 7 may not be necessary as not all subjects need 3 UV treatments, but each subjects will need 2 lock-ins.

#### **9.2.1. Preoperative**

At the preoperative exam, subjects will be consented, qualified for the study (compared with inclusion/exclusion criteria), and assigned a study ID/subject number. Subject numbers will be assigned sequentially at each site in the order of enrollment. Pre-operative qualification should take place no more than 90 days prior to surgery.

A medical history will be taken and exams will include the tests described below:

- manifest refraction,
- visual acuity

In addition, all site-specific, routine, usual standard of care preoperative measures should be undertaken.

Measurements should be made as described in section 9.3 below.

#### 9.2.2. Operative (Surgery)

All subjects will undergo cataract surgery with implantation of either the Clareon or LAL IOL. The surgeon's usual standard of care with regard to treatment and medication will be used for all study subjects.

All patients will undergo bilateral femtosecond laser assisted cataract surgery (with ORA in the Clareon group). Surgeries will be completed 1 week apart with the non-dominant eye being the first eye. Surgeries will include femtosecond laser arcuate keratotomy or Clareon monofocal/toric IOL power calculation targeting (dominant eye: Plano  $\pm$  0.25D; non-dominant eye: -0.75 ~ -1.00D). Personalized lens constants for Clareon and Clareon toric will be used with Barrett Universal II formula, Barrett toric calculator and will consider the results from Hill RBF. If discrepancy between ORA and Barrett Universal II, will adjust to first minus on sphere that ORA recommends and will adjust one T power up or down based on ORA.

LAL patients will have a pre-op target of closest to +0.25D calculated with the Barrett Universal II formula. LAL patients will undergo UV treatment until targeted refractive outcomes are achieved (dominant eye: plano  $\pm$  0.25D; non-dominant eye: -0.75 ~ -1.00D).

Surgical findings will be recorded and any adverse events/serious adverse events (AEs/ SAEs) occurring during surgery will be noted at this visit. Any other problems during surgery and comments regarding surgery will be documented.

Any subject whose surgery is not completed successfully will be documented in the appropriate case report form. These subjects will be monitored for safety but clinical performance data may be excluded from the analysis.

### **9.2.3. Postoperative Day 17 to 28**

All routine, usual standard of care postoperative measures should be undertaken. In addition, the subject will undergo VA, manifest refraction, PRSIQ questionnaire, and iTrace testing in accordance with the specifications below (Section 9.3). Adverse events will be monitored.

### **9.2.4. Postoperative UV Treatments**

LAL patients will undergo UV treatment until targeted refractive outcomes are achieved (dominant eye: plano  $\pm$  0.25D; non-dominant eye: -0.75 ~ -1.00D). All routine, usual standard of care postoperative measures should be undertaken. In addition, the subject will undergo VA, manifest refraction, and iTrace testing (Section 9.3) at these visits. Any device deficiencies or adverse events will be monitored.

### **9.2.5. Postoperative Day 90**

All routine, usual standard of care postoperative measures should be undertaken. In addition, the subject will undergo VA, manifest refraction, defocus curve, PRSIQ questionnaire, and iTrace testing (Section 9.3). Any device deficiencies or adverse events will be monitored.

### **9.2.6. Exit Procedures**

In the event of premature exit from the study, all study related examinations should be completed where possible. The Exit CRF should be completed, noting that the subject did not complete the study and the reason for premature study exit. If no premature exit from the study occurs, the Exit CRF should be completed at the end of Visit 7 (Postoperative Day 90).

## ***9.3. Study Methods and Measurements***

All routine testing and basic eye examinations should be carried out at each study visit. Abnormalities should be recorded in the CRF “Comment” section. Specific study examination procedures are outlined below.

### **9.3.1. Manifest Refraction**

Perform a manifest refraction with a high contrast logMAR chart under photopic lighting conditions ( $>85\text{ cd/m}^2$ ). Document refraction results with sphere, cylinder and axis readings. If uncorrected visual acuity is not improved by manifest refraction, use zero for sphere and cylinder and draw a line through the blank for the axis.

***Note:*** Each subject should be manually refracted to his/her best correction by an ophthalmologist, optometrist, or a skilled technician using a phoropter or trial lenses.

### **9.3.2. Visual Acuity (VA)**

To obtain logMAR VA, ask subjects to begin reading the chart at the smallest row where all letters are easily distinguishable. Have subjects continue to read rows with smaller letters and encourage subjects to guess at all letters in a line if at least one correct response was given on the previous row. Request subjects read rows until no letters on a row are read correctly or until all letters on a row are too indistinguishable to even be guessed.

While the subject is reading the chart, record the number of letters on each line read incorrectly by the subject. The last line from which the subject read at least one letter correctly is recorded as the baseline logMAR VA. The actual logMAR VA is calculated using the baseline logMAR VA line and the number of letters read incorrectly.

#### *Distance VA*

Measure distance visual acuity using a high contrast logMAR ETDRS chart under photopic lighting ( $>85 \text{ cd/m}^2$ ) at a distance of 4 m.

#### *Intermediate VA*

Have the subject view an appropriately-scaled high-contrast logMAR ETDRS Visual Acuity Chart at 66 cm. Visual acuity determined with the chart will be recorded and scored.

#### *Near VA*

Have the subject view an appropriately-scaled high-contrast logMAR ETDRS Visual Acuity Chart at 40 cm. Visual acuity determined with the chart will be recorded and scored.

#### 9.3.3 Defocus Curve

Perform monocular distance corrected (corrected to plano) and binocular defocus curve (dominant eye: plano corrected, non-dominant: -1.00) with a high contrast logMAR chart under photopic lighting conditions ( $>85 \text{ cd/m}^2$ ). Conduct testing with the manifest distance refraction in place in a phoropter. Add an over-correction of +1.0 D and record VA. Reduce the correction by +0.5 D and retest and record VA. Reduce the correction by +0.25 D and retest and record VA. Add an over-correction of -2.50 D and record VA. Remove over-correction in 0.5 D increments while testing VA at each step (also be sure to record the VA at -0.25 D). The procedure ends with VA testing at a 0.0 D over-correction (best-corrected distance refraction).

#### 9.3.3 Questionnaires

The Patient reported spectacle usage questionnaire (PRSIQ) will be administered to subjects. The administrator should ensure the subjects understand the nature of the questions but should not interpret them for the subject.

#### ***9.4. Unscheduled Visits***

Unscheduled exams may be conducted at the discretion of the Investigator with all relevant information from the exam recorded in the source documents and on the Unscheduled Visit pages within the CRF booklet.

#### ***9.5. Discontinued Subjects***

Discontinued subjects are those who do not have an exit visit or who come into the office to be exited prior to the scheduled final study visit. Subjects may be discontinued from the study at any time if, in the opinion of the investigator, their continued participation in the study poses a risk to their health. The reasons for discontinuation include:

- a. Adverse event;
- b. Lost to follow-up;
- c. Subject decision unrelated to an adverse event;
- d. Protocol violation;
- e. Treatment failure;
- f. Other.

To ensure the safety of all subjects who discontinue prior to Visit 8, investigators should assess each subject and, if necessary, advise them of any therapies and/or medical procedures that might be needed to maintain their health. Any changes in medical health and/or use of concomitant medications should also be captured.

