### **10. ANALYSIS PLAN**

#### ***10.1. Analysis Data Sets***

All subjects who are enrolled in the study will be evaluated for safety. Efficacy analyses will be performed based on data from those eyes where uncomplicated cataract surgery with IOL implantation was completed.

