##### **10.2.1. Within-treatment Changes**

For variables measured on a continuous scale, these summaries will include the sample size, as well as the mean, standard deviation, median, minimum, and maximum. For variables measured on a categorical scale, summaries will provide the number and percentage of eyes in each category. These summaries will be provided for all eyes completing the study.

Differences between parametric variables will be compared using a two-sample t-test. Differences between categorical variables will be compared using the 2-sample test for equality of proportions.

For non-inferiority testing, if the upper boundary of the 95th confidence interval is not greater than 0.1 logMAR, non-inferiority will be claimed.

The step-down methodology will be used on the non-inferiority endpoints in the following order:

- 1) Binocular CDVA
- 2) Binocular DCIVA
- 3) Binocular UDVA
- 4) Binocular UIVA

The correlation of total ocular and internal HOAs (especially SA) with monocular DCIVA will be evaluated using regression modelling. Findings from these models will provide an indication of whether any HOAs are statistically significantly associated with post-op DCIVA, and the strength of any such association.

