## **18. STUDY ENDPOINT CRITERIA**

### ***18.1. Patient Completion of Study***

If a study patient has completed the final visit (Visit 8) of the study, he/she is considered to have completed the study.

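### Undefined exit reasons (9.5), mandatory exit for non-compliance (18.2) and completers-only summaries (10.2.1) let subjects drop out of the 3-month comparison, possibly in relation to outcome

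*Combined protocol and SAP*

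**What the plan says.** **Exit reasons.** Section 9.5 gives one criterion for exit on the investigator's initiative: that "in the opinion of the investigator, their continued participation in the study poses a risk to their health". It then lists six reasons, among them "d. Protocol violation" and "e. Treatment failure". Neither term is defined anywhere in the document.

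**Other exit rules.** Section 18.2 makes discontinuation mandatory for administrative reasons and gives non-compliance and not keeping to the visit schedule as examples. It attaches no health condition, and it replaces only subjects lost before surgery. Section 18.3 ends participation after a severe adverse event that may be study-related, and counts that subject as having completed.

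**Data at exit.** Section 9.2.6 says: "In the event of premature exit from the study, all study related examinations should be completed where possible".

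**Analysis.** Section 10.1 states: "Efficacy analyses will be performed based on data from those eyes where uncomplicated cataract surgery with IOL implantation was completed". Section 10.2.1 adds: "These summaries will be provided for all eyes completing the study". Section 18.1 defines completion: "If a study patient has completed the final visit (Visit 8) of the study, he/she is considered to have completed the study". No all-randomised analysis, missing-data method or sensitivity analysis is stated. Section 3 records that there is no masking.

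**The concern.** The lenses are implanted once and the endpoints are acuities at 3 months. Apart from the light adjustments in the LAL arm, no study treatment remains to be stopped after surgery. A disappointing refractive or visual result is therefore outcome data, and an exit coded as treatment failure would lose the very observation the trial is meant to collect.

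Staff who know the lens apply an undefined term, and the subject then has no stated place in the efficacy results. If exits relate to outcome and differ between arms, the comparison is biased. Losing poor Clareon results favours the non-inferiority claim; losing poor LAL results works against it.

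The endpoints are not equally exposed. An off-target refraction acts directly on UDVA and UIVA, which are steps 3 and 4 of the step-down order. Binocular CDVA, the primary, is measured with the refractive error corrected and should be little affected.

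The arms also differ in how often exit could arise. LAL subjects have Visits 4 to 7 (6 and 7 only if needed) in addition to the visits shared with Clareon, so they have more occasions to miss a visit or be judged off target. Losses therefore need not cancel, although nothing in the documents shows that they will differ.

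**Working it through.** **1. Follow one subject through the text.** Take a subject with uncomplicated surgery in both eyes who exits on day 40 with the code protocol violation or treatment failure.
- 10.1: the eyes qualify for the efficacy set.
- 9.2.6: an examination is done at exit if possible. It gives a day-40 acuity, whereas the final visit is at day 90 ± 14.
- 18.1 and 10.2.1: Visit 8 was not attended, so the eyes are not among those summarised.
- No section carries the exit value forward, imputes a 3-month value or tests sensitivity to its absence.

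The subject is nominally in the efficacy set but contributes nothing to the 3-month comparison. Section 18.3 adds an inconsistency: a subject terminated under it counts as a completer but may have no Visit 8 acuity.

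**2. Reproduce the plan's own figure.** Section 11 assumes a difference of 0.05 and an SD of 0.1; the margin is 0.1 (section 3). With power 90% and one-sided alpha 0.05:

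n = 2 × (1.645 + 1.282)² × 0.1² / (0.1 − 0.05)² = 68.5, rounded up to 69 per group.

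This matches the stated 69. One-sided 0.025 would give 85. The sidedness is not stated, and 69 contains no dropout allowance.

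**3. Illustrative shift in one arm.** Assumptions not in the documents: k of 69 subjects are lost, all from one arm, and each is on average d = 0.2 logMAR worse than those retained.

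Shift in that arm's observed mean = (k/69) × d.
- k = 3 (4.3%): 3/69 × 0.2 = 0.0087
- k = 7 (10.1%): 7/69 × 0.2 = 0.0203

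Against the 0.05 gap between assumed difference and margin, that is 0.0087/0.05 = 17% and 0.0203/0.05 = 41%. Section 11 does not say which acuity the 0.05 and 0.1 describe, so applying the gap to UDVA is itself an assumption.

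**4. Worst case favouring the claim.** Simulation (50,000 runs): normal acuity, SD 0.1, the worst k Clareon subjects removed, LAL arm intact, true difference equal to the margin.

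| k removed | Shift in Clareon mean | False non-inferiority, one-sided 0.05 | One-sided 0.025 |
|---|---|---|---|
| 0 | 0 | 5.0% | 2.5% |
| 1 | 0.003 | 7.8% | 4.1% |
| 3 | 0.009 | 14.6% | 8.7% |
| 5 | 0.014 | 22.9% | 14.9% |
| 7 | 0.019 | 32.7% | 22.6% |

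The simulated shifts imply that the removed subjects are 0.0092 × 69/3 = 0.21 (k = 3) and 0.0192 × 69/7 = 0.19 (k = 7) logMAR worse than the full-arm mean. So with SD 0.1, the 0.2 used in step 3 is roughly what losing the very worst subjects would mean. It is an extreme value.

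**5. The opposite direction.** The same shift in the LAL arm narrows the gap to the margin. Standard error = 0.1 × √(2/69) = 0.0170, held fixed for simplicity. Power at one-sided 0.05 is Φ(gap/0.0170 − 1.645):
- no loss, gap 0.05: 90%
- k = 3, gap 0.0413: 78%
- k = 7, gap 0.0297: 54%

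**6. Loss unrelated to outcome.** Losing 7 per arm at random only lowers power: from 90.2% to 87.3% at one-sided 0.05, or from 83.6% to 79.5% at one-sided 0.025.

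**The case against.** A reader might infer that 9.5 licenses unmasked investigators to remove poor results before the 3-month visit. The text does not support that. The only authority it gives the investigator is health risk. The six-item list mixes events nobody chooses (loss to follow-up), subject decisions and a residual category, so it reads largely as codes for recording why a subject left. Nothing defines treatment failure as a missed target or poor acuity. In the LAL arm the stated response to a missed target is more light treatment, not exit: "LAL patients will undergo UV treatment until targeted refractive outcomes are achieved". Section 9.2.2 gives both arms the same refractive targets. All of this stands, and no intent to remove subjects can be read into the plan.

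It is also fair that 9.2.6 preserves some data, that the illustration bears on uncorrected acuity more than on the primary endpoint, and that its inputs are assumed.

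The gap remains even so. Health risk is not the only route out, because 18.2 makes exit mandatory for non-compliance. Even as a mere code, treatment failure presupposes that subjects leave for that reason, and nothing asks staff to keep them to Visit 8. An early-exit examination is not a 3-month acuity, and no rule brings it into the analysis.

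**Conclusion.** The point holds as a gap between sections. Undefined exit reasons in 9.5, mandatory exit in 18.2, completers-only summaries in 10.2.1 and the absence of masking and of any missing-data rule together allow outcome-related loss of 3-month data. Bias could go either way and falls mainly on UDVA and UIVA rather than primary CDVA.

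Its size cannot be known, because no exit or failure rate is given. The 0.009 to 0.020 logMAR shift rests on three assumptions: 3 to 7 losses, all in one arm, each about 0.2 logMAR worse. The error rates in step 4 are a ceiling under perfectly selective one-arm removal. Neither set of figures is a forecast, and the 17% to 41% should not be read as the bias expected in the primary result. The case for acting is that the correction is cheap and removes the question.

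**What to change.** 1. Reconcile 9.5, 18.2 and 18.3 so that they state one consistent set of conditions for leaving the study, and settle whether a subject terminated under 18.3 counts as completing. Which clinical conditions should end participation is for the sponsor and investigator to decide.
2. Add to 9.5: *A missed refractive target, poor acuity, a protocol violation or non-compliance is recorded on the CRF and does not by itself end data collection. Unless consent is withdrawn, the subject is lost to follow-up or continuing poses a health risk, the subject is followed to Visit 8 and analysed in the randomised group.*
3. Align 10.1 and 10.2.1 with that sentence, and state how subjects without a Visit 8 acuity are handled, with a sensitivity analysis.
4. Report exit reasons by arm. Items d and e may stay as descriptive codes if treatment failure and protocol violation are defined. Deleting them would not be enough, since the residual category in 9.5, the mandatory rule in 18.2 and the power in 7.3 to declare a patient non-evaluable would remain.

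Cost: a few sentences, with no new visits or staff. The downside is that reported acuity may look slightly worse.

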### **10. ANALYSIS PLAN**

#### ***10.1. Analysis Data Sets***

All subjects who are enrolled in the study will be evaluated for safety. Efficacy analyses will be performed based on data from those eyes where uncomplicated cataract surgery with IOL implantation was completed.

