## 7. SUBJECTS

### 7.1. *Subject Population*

Eligible test subjects will be adult normal astigmatic ( $\geq 0.75$ D corneal astigmatism) cataract patients presenting for cataract surgery who are considered appropriate candidates for intraocular lens implantation.

A total of 138 subjects at one site will be enrolled (69 per group). Both eyes of a subject must be enrolled. Subjects must meet the inclusion criteria. Prior to enrollment, subjects will be provided information on the study and asked to sign a patient information and consent form to participate. The patient information and consent form will be approved by an appropriate ethics committee.

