## 8. STUDY DESIGN

### 8.1. ***Study Design***

This study is a single center, multi-surgeon, prospective, randomized, comparative study of binocular corrected distance visual acuity (CDVA) after successful bilateral cataract surgery. Subjects will be assessed pre-operatively, operatively and at up to 6 post-operative visits. Clinical evaluations will include administration of patient reported spectacle usage questionnaire (PRSIQ), as well as measurement of monocular and binocular visual acuities at distance, intermediate, and near, defocus curve, manifest refraction, measurement of higher order aberrations.

The primary outcome measure will be the binocular corrected distance visual acuity (CDVA), 3-months postop.

Secondary outcome measures are as follows:

- Binocular uncorrected distance visual acuity (UDVA), 3-months postop.
- Binocular distance-corrected intermediate visual acuity (DCIVA) at 66cm, 3-months postop.
- Binocular uncorrected intermediate visual acuity (UIVA) at 66cm, 3-months postop.
- Monocular corrected distance visual acuity (CDVA), 3-months postop.
- Monocular uncorrected distance visual acuity (UDVA), 3-months postop.

- Monocular distance-corrected intermediate visual acuity (DCIVA) at 66cm, 3-months postop.
- Monocular uncorrected intermediate visual acuity (UIVA) at 66cm, 3-months postop.

Exploratory outcome measures are as follows:

- Binocular distance-corrected near visual acuity (DCNVA) at 40cm, 3-months postop.
- Binocular uncorrected near visual acuity (UNVA) at 40cm, 3-months postop.
- Monocular distance corrected defocus curve at 3 months post-op for both eyes in LAL group and dominant eye for Clareon group.
- Binocular defocus curve at 3 months post-op (dominant eye: plano corrected, non-dominant: -1.00D)
- Manifest refraction (MRSE, residual sphere, and residual astigmatism) at postoperative day 17-28 and at 3 months post-op.
- Patient reported spectacle usage questionnaire (PRSIQ) at postoperative day 17-28 and at 3 months post-op
- Total ocular, corneal and internal HOA and SA with iTRACE for both eyes in LAL group and dominant eye for Clareon group (Objective depth of focus measurement with iTRACE for each eyes in both groups).
- Number of days and post-op office visits from cataract surgery to routine "release of care visit" (i.e. final lock-in for LAL group, 17-28 days after 2nd eye surgery for Clareon group).

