### ***18.3. Patient Termination***

A study patient will be terminated if the study patient develops any severe adverse event that may be related to the study. A study patient will receive appropriate treatment at the discretion of the investigator. Notification of termination will be clearly documented. These study patients are considered to have completed the study and will not be replaced.

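### All efficacy analyses, including the primary non-inferiority test, are confined to eyes with uncomplicated surgery, and no as-randomised test is planned beside them

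*Combined protocol and SAP*

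**What the plan says.** Section 10.1 gives one rule for safety and one for efficacy. For safety, "All subjects who are enrolled in the study will be evaluated for safety". For efficacy, "Efficacy analyses will be performed based on data from those eyes where uncomplicated cataract surgery with IOL implantation was completed". No other efficacy set is named for hypothesis tests.

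Section 9.2.2 deals with failed surgery: "Any subject whose surgery is not completed successfully will be documented in the appropriate case report form", and then "These subjects will be monitored for safety but clinical performance data may be excluded from the analysis". Section 7.3 lets the principal investigator declare a patient non-evaluable on medical evidence and sets no time limit. Section 3 gives masking as none.

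Section 8.1 describes a "comparative study of binocular corrected distance visual acuity (CDVA) after successful bilateral cataract surgery", and section 7.1 says "Both eyes of a subject must be enrolled". In section 10.2.1, "The step-down methodology will be used on the non-inferiority endpoints in the following order", and all four listed endpoints are binocular, with binocular CDVA (the primary) first. Non-inferiority is claimed if the upper confidence limit does not exceed 0.1 logMAR.

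Some passages bear on attrition. Section 10.2.1 has summaries report sample sizes and cover every eye that completes the study. Section 9.2.6 asks for study examinations where possible at an early exit, with the reason recorded. Under section 18.3, subjects with a severe, possibly related adverse event are terminated, and "These study patients are considered to have completed the study and will not be replaced". No rule covers missing Visit 8 acuity.

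**The concern.** Randomisation makes the arms comparable at assignment. A set defined by how surgery went is formed later. If the arms lose different shares of subjects, or subjects with different acuity, the comparison is no longer the randomised one. The protocol does not state when randomisation takes place. Section 9.2.2 gives the arms different planning targets and intraoperative steps, however, so assignment must precede surgery.

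Two features add to this. The words permitting exclusion are permissive rather than mandatory, in a trial where everyone knows the arm. The set is also worded by eye, whereas each step-down endpoint has one value per subject. Sections 7.1 and 8.1 suggest that both eyes must qualify, but section 10.1 does not say so.

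At stake is the primary claim. Removing more poor outcomes from Clareon favours non-inferiority, and removing more from LAL works against it. The plan has no test that would show whether the conclusion survives when those subjects are put back.

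**Working it through.** **Inputs from the protocol.** Margin 0.1 logMAR (sections 3 and 10.2.1). Assumed true difference 0.05, SD 0.1, power 90%, alpha 0.05, 69 per group (section 11). The sidedness of alpha and of the confidence interval is not stated, so both readings are shown. Differences are Clareon minus LAL; positive means Clareon is worse.

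**Assumed inputs (not in the protocol).** Exclusions of 5% against 3%, in either direction, and 4% in each arm for the cost calculation. Excluded subjects are 0.1 to 0.3 logMAR worse in binocular CDVA than those kept.

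**Step 1: reproduce the plan's figure.** n = 2 × SD² × (z for alpha + z for power)² / (margin − difference)².
- One-sided 0.05: 2 × 0.01 × (1.645 + 1.282)² / 0.05² = 68.5, so 69. This matches.
- One-sided 0.025: 2 × 0.01 × (1.960 + 1.282)² / 0.05² = 84.1, so 85. This does not match.

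**Step 2: shift caused by exclusion.** Removing a fraction p of an arm, whose mean is worse than the rest by g, lowers that arm's mean by p × g. The change in Clareon minus LAL is therefore −(p in Clareon − p in LAL) × g. With 5% against 3%:
- 0.02 × 0.1 = 0.002
- 0.02 × 0.2 = 0.004
- 0.02 × 0.3 = 0.006

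With equal fractions and equal losses the shift is zero.

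**Step 3: effect on the claim.** The standard error is 0.1 × √(2/69) = 0.0170. Claim rates come from the noncentral t distribution with 136 degrees of freedom.

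| Shift | True difference 0.1, one-sided 0.05 | True difference 0.1, two-sided 95% interval |
|---|---|---|
| none | 5.0% | 2.5% |
| −0.002 | 6.3% | 3.3% |
| −0.004 | 7.9% | 4.2% |
| −0.006 | 9.8% | 5.4% |
| +0.002 | 3.9% | 1.9% |
| +0.004 | 3.0% | 1.4% |
| +0.006 | 2.3% | 1.0% |

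A normal approximation checks the −0.006 row: 0.006 / 0.0170 = 0.35, and the lower tail at −1.645 + 0.35 is about 9.8%.

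With the imbalance reversed (3% Clareon, 5% LAL) and a true difference of 0.05, power falls from 90% to 82–88% (one-sided 0.05) or from 83% to 73–80% (two-sided 95% interval). Reducing n for the excluded subjects changes the false-claim rates by at most about 0.001 and lowers power by a further 0.01 to 0.02.

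**Step 4: cost of the as-randomised analysis.** Assume 4% complicated in each arm. The as-randomised SD is √(0.01 + 0.04 × 0.96 × g²), which is 0.102, 0.107 and 0.116 for g = 0.1, 0.2 and 0.3. The two-sided 95% half-widths are 0.034, 0.036 and 0.039, against 0.034 in the restricted set. By simulation at g = 0.3 and a true difference of 0.05, power is about 81% as-randomised against 88–89% restricted (one-sided 0.05), or about 71% against 82% (two-sided 95% interval). About 10% and 13% of trials, respectively, pass only the restricted analysis.

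**The case against.** The restricted set is defensible. It matches the successful-surgery population of section 8.1, and the false-claim rates above refer to all randomised subjects instead. Some complaint about the set is therefore a preference for a different target. This stands, and it is why the set should be kept. It does not answer the need for a second analysis, because comparability within a set chosen after assignment is not guaranteed by randomisation.

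A reader might infer that the report would hide the exclusions altogether. The protocol does not support that. Failed surgery goes on a CRF, summaries give sample sizes and cover eyes completing the study, exit examinations are sought, and safety covers everyone enrolled. These sources would show some attrition descriptively. They do not test whether the non-inferiority result depends on it, and exit examinations would not supply 3-month acuity after an early exit.

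A reader might also infer that the plan is tilted towards Clareon. The protocol gives no complication rates and shows no difference by arm. All patients have femtosecond laser assisted surgery, and eligibility requires a dilated pupil of at least 7 mm and excludes zonular problems and pseudoexfoliation. The illustrated shift is only 2 to 6% of the margin.

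Finally, an as-randomised analysis limited to subjects with Visit 8 acuity still depends on something that happens after assignment. That is correct, and it is the reason for adding a missing-data sensitivity analysis.

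**Conclusion.** The concern holds as a gap in the analysis plan. The primary non-inferiority test rests on one set, fixed after assignment and partly by discretion in an unmasked trial, with no as-randomised test beside it. Bias is possible in either direction and is not demonstrated. The absent definition of uncomplicated surgery is a missing detail, not the main point.

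Under the assumed 5% against 3% exclusions the effect is modest: a shift of 0.002 to 0.006 logMAR, which at most roughly doubles the false-claim rate at the margin. It is zero when exclusions and losses balance, and larger if exclusions fall in one arm only. These figures rest on invented exclusion rates and losses, SD 0.1 and 69 per group, which the blinded re-estimation in section 11 may change. The change should be made because it is cheap, and because fixing exclusions before acuity is seen cannot be done afterwards.

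**What to change.** In section 10.1, add a subject-level analysis of binocular CDVA in all randomised subjects, in the assigned arm and whatever the surgical course, against the same 0.1 margin. Add one simple pre-specified sensitivity analysis for missing Visit 8 acuity, for example imputation within arm, repeated with imputed Clareon values made 0.1 logMAR worse. Report this beside the restricted analysis and discuss any disagreement; passing both need not be required.

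Keep the restricted set, but apply it by subject for the binocular endpoints, with both eyes qualifying. For analysis purposes, replace the permissive exclusion wording in section 9.2.2 and the open non-evaluable right in section 7.3 with exclusions fixed before Visit 8 acuity is seen. Report exclusions, with reasons, by arm.

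The cost is wording in sections 7.3, 9.2.2 and 10.1 and two further analyses, mostly from data already collected, with no extra subjects or visits. The as-randomised result can be less precise, as step 4 shows, and the two analyses will sometimes disagree by chance even when exclusions are balanced.
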